#### 9.4. ANALYSIS OF SERUM CONCENTRATIONS

# 9.4.1. Summary of Trough Concentrations for Total IgG, and IgG Subclasses 1-4 (PK Trough Set).

Trough concentrations measured by local lab (Total IgG) and by central lab (IgG subclasses) will be summarized for each type of analyte (total IgG, subclasses of IgG) by dosing regimen (Q3W, Q4W), whole population, each age category, and visits, combining all dose levels including baseline values for prior IVIG formulations used by subjects before start of treatment with BT595 to study. Additional summaries will also be provided by dose level divided into 3 bins (0.2-<0.4, 0.4-<0.6, 0.6-0.8 g/kg dose bins) according to dosing regimen. Based on the number of subjects per age category the summaries by dose level may combine all or specific age categories, e.g., pediatric vs adult to have sufficient number of data for descriptive statistics.

Age categories are based on FDA (FDA, 2016) and EMA (EMA/CHMP/BPWP/94033/2007 rev. 2) guidance for IVIG. Additionally FDA and EMA guidance on pediatric studies and PK in pediatric studies were taken into consideration for planning of PK analyses [Food and Drug Administration (FDA) Guidance for Industry: General Clinical Pharmacology Considerations for Pediatric Studies for Drugs and Biological Products. December 2014. Available from: http://www.fdanews.com/ext/resources/files/12-14/12-08-14pediatricguidance.pdf?1418077303; European Medicines Agency Guideline ICH Topic E 11 Clinical Investigation of Medicinal Products in the Paediatric Population. January 2001. Available from:

http://www.ema.europa.eu/docs/en\_GB/document\_library/Scientific\_guideline/2009/09/W C500002926.pdf; European Medicines Agency Guideline On The Role Of Pharmacokinetics In The Development Of Medicinal Products In The Paediatric

Population. June 2006. Available from:

http://www.ema.europa.eu/docs/en\_GB/document\_library/Scientific\_guideline/2009/09/W C500003066.pdf].

Summary statistics will not be presented if 50% or more of the actual values for the PK sets at any 1 time point or bin are BLQ or missing or less than 3 values are available. The reporting will be limited to median value for n=1 and to median, min and max values for  $1 < n \le 2$ .

In addition, for the IgG subclasses, each individual concentrations (g/L) will be transformed to relative proportion of the total of the 4 subclasses (percent of the total). Individual percentage will be listed in same table reporting the concentrations (g(L) and summarized separately for the Q3W and Q4W regimen (all subjects and all dose together).

Evaluation of total IgG trough levels will include the calculation of the proportion of subjects who failed to meet the total IgG target level ( $\geq$ 5 g/L) prior to dose adjustment (Section 8.2.1), and an intra individual comparison to trough levels of the former IVIg product (i.e., using baseline data before 1st infusion of BT595, see Section 9.7).

Additionally, trough concentrations measured by local lab (Total IgG) and central lab (IgG subclasses) will be summarized by age categories based on FDA and EMA requirements:

Analyte	Schedule	Age category (years)	Visit
Total IgG	Q3W Q4W	2 to <6 (EMA, FDA) 6 to <12 (EMA, FDA) 12 to <17 (FDA) 12 to <18 (EMA) 2 to <17 (FDA) 2 to <18 (EMA) 17 to <76 (FDA) 18 to <76 (FDA) 18 to <76 (EMA) 17 to <65 (FDA) 18 to <65 (EMA) >=65 (EMA, FDA) Overall: 2 to <76	V1 to V20 according to dosing schedule
IgG subclasses	Q3W Q4W	6 to <12 (EMA, FDA) 12 to <17 (FDA) 12 to <18 (EMA) 6 to <17 (FDA) 6 to <18 (EMA) 17 to <76 (FDA) 18 to <76 (EMA) 17 to <65 (FDA) 18 to <65 (EMA) >=65 (EMA, FDA) Overall: 6 to <76	V1 (baseline) and V7/V5 (before the 7 th /5 th infusion)

Finally, trough concentrations measured by local lab (Total IgG) and central lab (IgG subclasses) will be summarized by dose level for last infusion:

Version Final 2.0

Analyte	Schedule	Age	Visit	Dose levels
		category		
Total IgG	-Q3W	All: 2 to <76	V1 to V20	0.2-<0.4
	-Q4W	Pediatric vs adult:	according to	0.4-<0.6
	-Combined	2 to <17 and 17 to <76	dosing	0.6-0.8
		(FDA)	schedule	
		2 to <17 and 17 to <65		
		(FDA)		
		2 to <18 and 18 to <76		
		(EMA)		
		2 to <18 and 18 to <65		
		(EMA)		
lgG	Q3W	All: 6 to <76	V1 (baseline)	0.2-<0.4
subclasses	Q4W	Pediatric vs adult:	and V7/V5	0.4-<0.6
		6 to <17 and 17 to <76	(before the	0.6-0.8
		(FDA)	7th/5th	
		6 to <17 and 17 to <65	infusion)	
		(FDA)		
		6 to <18 and 18 to <76		
		(EMA)		
		6 to <18 and 18 to <65		
		(EMA)		

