7 COURSE OF THE CLINICAL STUDY

7.1 Visit Schedule

Screening Visit (Visit 1, Week -4 to 0, Day -28 through Day 0)

All subjects will attend a screening visit up to 4 weeks before the first BT595 infusion, where the following procedures will be performed:

- Written informed consent/assent will be obtained.
- Demographic data (including gender, date of birth [for calculation of age; note: age will be the age recorded at screening], ethnic origin, height, and body weight) will be recorded.
- Medical and surgical history with regard to the subjects' drug history, • previous medication, disease (i.e., PID) history, and other medical and surgical history will be recorded. Previous medication data up to 4 weeks before enrollment will be recorded, with the exception of data on the subject's established replacement therapy (at least 6 months before study enrollment) and data on blood-derived medication (i.e., administration of blood or blood products; at least 3 months before study enrollment). The type of previous medication, dose schedule, duration, and the indication the previous medication was given for will be documented. An x-ray may be performed at any time throughout the study to evaluate new observations against baseline findings, if medically indicated, and to confirm diagnostic criteria for acute serious bacterial infections. This is not applicable for Germany. (Note: if the subject has recently had an x-ray taken [i.e., within the last 3 months before study start], this result may be considered as baseline data).
- Eligibility to take part in the study will be assessed against the inclusion and exclusion criteria.
- A physical examination will be performed.
- Vital signs (pulse, blood pressure, temperature, respiratory rate) will be recorded.

•

- A serum pregnancy test (human chorionic gonadotropin) will be performed for all female subjects of child-bearing potential (\geq 12 years of age or presence of menstruation at screening).
- Samples for routine safety laboratory parameters (hematology, coagulation, clinical chemistry, urinalysis) will be taken.
- Samples for intravascular hemolysis laboratory parameters (including Coombs' test, haptoglobin, hemoglobin, hemosiderin) will be taken.
- Retention samples for viral safety laboratory parameters will be taken.
- Samples for virus serology laboratory parameters (hepatitis B, hepatitis C, HIV) will be taken.
- Samples for IgG trough levels (total IgG) will be taken.

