Baseline Visit (Visit 2, Week 0, Day 1)

All subjects will attend a baseline visit on Day 1, where the following assessments will be performed 3 or 4 weeks (depending on the subject's treatment schedule) after the last infusion of the subject's previous IVIg replacement therapy and before the subject's first BT595 infusion (unless indicated):

- Any changes in medical and surgical history with regard to the subjects' drug history, previous medications, disease (i.e., PID) history, and other medical and surgical history since the screening visit will be recorded. The type of previous medication, dose schedule, duration, and the indication the previous medication was given for will be documented. (Note: if the subject has recently had an x-ray taken [i.e., within the last 3 months before study start], this result may be considered as baseline data).
- Eligibility to take part in the study will be confirmed against the inclusion and exclusion criteria, as appropriate (i.e., diagnostic tests will be repeated at the investigator's discretion).
- A physical examination will be performed.
- Vital signs (pulse, blood pressure, respiratory rate) will be recorded within 30 minutes before the infusion, 15-30 minutes after the start of infusion, 15-30 minutes after the end of infusion, and 15-30 minutes after the start of any change in the infusion rate. Temperature will only be recorded within 30 minutes before the infusion.
- Body weight will be recorded (to calculate subject dose).
- A urine pregnancy test (dipstick) will be performed for all female subjects of child-bearing potential (≥12 years of age or presence of menstruation at screening).
- Samples for routine safety laboratory parameters (hematology, coagulation, clinical chemistry, urinalysis) will be taken.
- An additional sample for routine safety laboratory parameters (hematology, coagulation, clinical chemistry, urinalysis) will be taken at the end of the first BT595 infusion.
- Samples for IgG trough levels (total IgG) will be taken.
- An additional sample for total IgG will be taken at the end of the first BT595 infusion.
- Samples for IgG trough levels (IgG subclasses 1-4) will be taken (with the exception of pediatric subjects [2-5 years, inclusive]).
- Samples for IgG trough levels (specific antibody levels) will be taken (with the exception of pediatric subjects [2-11 years, inclusive]).

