#### Definition of Baseline

Baseline will be defined as the last available value before the first infusion of study medication and may be any visit between screening and day 1 (including the baseline visit [V2]) and unscheduled visit.

Duration of concomitant antibiotic treatment

If medication starts before date of first infusion (Visit 2, Day 1): Duration of concomitant antibiotic treatment [days] = Date of stop of antibiotic treatment – Date of first infusion +1.

If medication starts at/after date of first infusion (Visit 2, Day 1):

Duration of concomitant antibiotic treatment [days] = Date of stop of antibiotic treatment – Date of start of antibiotic treatment + 1

Duration of infusional AE

Duration of AE [hours] = (Date/time of stop of AE – Date/time of start of AE)

Duration of noninfusional AE

Duration of AE [days] = Date of stop of AE – Date of start of AE + 1

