#### 7.2. DEMOGRAPHIC AND OTHER BASELINE CHARACTERISTICS

Demographic (age, gender, height, weight, BMI and race) and baseline characteristics (e.g. child-bearing potential status, IgG trough level at screening, IgG trough level at baseline, IgG trough levels of specific antibody levels at baseline, IgG trough levels (subclasses 1-4)) will be presented in a summary table and a listing.

The summary table will be based on the FAS, PK Trough set, Specific IgG Trough PK set, Dense PK Subset and PPS, if applicable.

Age will be summarized as both a continuous variable and using the subgroup categories defined in Section 6.6.

All data will be listed.

Viral serology data (HIV, hepatitis B and hepatitis C) collected at screening (initial visit) will be listed only.

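### SAP 9.4.1 tabulates the screening (V1) total IgG value as a trough and SAP 6.2 lets it stand in as baseline, but nothing ties that sample to the end of the previous IVIg interval

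*SAP*

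**What the plan says.** Protocol 7.1 gives the screening window as "Screening Visit (Visit 1, Week -4 to 0, Day -28 through Day 0" and states that "All subjects will attend a screening visit up to 4 weeks before the first BT595 infusion". Among the screening procedures it lists "Samples for IgG trough levels (total IgG) will be taken". It gives no time since the subject's last infusion of the previous product.

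The same section does fix the baseline visit (V2, Day 1). Its assessments take place "3 or 4 weeks (depending on the subject's treatment schedule) after the last infusion of the subject's previous IVIg replacement therapy", before the first BT595 infusion, and include total IgG.

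The SAP then uses these samples as follows:

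- **6.2:** "Baseline will be defined as the last available value before the first infusion of study medication and may be any visit between screening" (the range closes on Day 1, and unscheduled visits count).
- **7.2:** "IgG trough level at screening" is reported as a baseline characteristic, next to the baseline trough.
- **9.4.1:** total IgG troughs are summarised for "V1 to V20 according to dosing schedule". The subclass rows of the same tables instead label V1 as baseline and pair it with V7/V5 for the 7th/5th infusion.
- **9.3, Table 1:** total IgG time points in the PK Trough Set are baseline, end of first infusion, and predose for all infusions. Screening is not listed.
- **9.6.3:** baseline is described as the trough of the product used before the study.
- **8.2.1 and 9.7:** baseline is the reference for change in trough IgG, and for the exploratory comparison of BT595 with the previous product against 80% to 125%.

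**The concern.** Under regular dosing IgG falls between infusions, so a sample drawn before the end of the interval is expected to lie above the trough. Screening has no rule placing it at the end of an interval, yet its value appears under a trough heading and may become the baseline.

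Two outputs are at stake. The V1 column, and the SAP 7.2 screening figure, can present mid-interval concentrations as troughs of the former product, for every subject with a screening value. Where V2 is missing, a V1 value can also become the reference in 8.2.1 and 9.7. An inflated reference would make BT595 troughs look lower than they are.

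**Working it through.** The plan gives no figure to reproduce here. The check has four parts.

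**1. Which visit is V1?** In the flowchart V2 is Week 0, so visit n falls at week (n − 2) × interval. V20 is (20 − 2) × 3 = Week 54 on the 3-week schedule, and V16 is (16 − 2) × 4 = Week 56 on the 4-week schedule. Both match the closing visits. Infusions run from V2 to V19, which is 18 on the 3-week schedule, so a range ending at V20 cannot be infusion numbering. V1 in the total IgG rows is therefore screening. The subclass rows do not fit flowchart numbering: baseline is V2, the 7th infusion (Week 18) is V8, and the 5th (Week 16) is V6. One table uses two numbering systems.

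**2. Where can V1 fall in the previous interval?** With V2 on Day 1, prior infusions fall on Day 1 − interval and earlier.

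| Schedule | Prior infusion in window | Days since prior infusion, Day -28 to Day 0 |
|---|---|---|
| 3-week | Day -20 | 13–20, infusion day, then 1–20 |
| 4-week | Day -27 | 27, infusion day, then 1–27 |

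Any point in the interval is possible, including one at or near trough.

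**3. How far above trough?** Assume mono-exponential decline and no endogenous IgG. The documents give no IgG half-life T, so I take T = 21 to 42 days. With interval τ and k = ln 2 / T:

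- Concentration at day t relative to trough: 2^((τ − t)/T).
- Arithmetic mean for a draw uniform over the interval: (e^(kτ) − 1)/(kτ).
- Geometric mean for the same draw, equal to the mid-interval value: 2^(τ/(2T)).

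| Schedule | Arithmetic mean, T = 42 to 21 | Geometric mean, T = 42 to 21 |
|---|---|---|
| 3-week (τ = 21) | 1.20 to 1.44 | 1.19 to 1.41 |
| 4-week (τ = 28) | 1.27 to 1.65 | 1.26 to 1.59 |

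The actual 3-week window counts late-interval days twice. Averaged over Day -28 to Day 0 at T = 30 days, the 3-week mean is about 1.25 (1.23 if the infusion-day sample precedes the infusion), against 1.29 for a uniform draw. A V2 pre-infusion sample has factor 1.00 by definition.

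**4. Effect on the comparison in 9.7.** Let a share f of subjects fall back to V1, with geometric mean inflation g. A true geometric mean ratio of 1.00 becomes g^(−f).

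| Situation | f | Ratio |
|---|---|---|
| 5% fall back, either schedule | 0.05 | 0.98 to 0.99 |
| 10% fall back, either schedule | 0.10 | 0.96 to 0.98 |
| One of five, 4-week cell | 1/5 | 0.91 to 0.95 |
| One of three, 4-week cell | 1/3 | 0.86 to 0.93 |

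For example, 1.59^(−1/3) = 0.86 and 1.26^(−1/3) = 0.93. The shares and cell sizes are illustrations, since the documents give no rate of missing V2 values. SAP 9.7 runs the comparison by dosing interval and, where possible, by age category, so small cells are plausible.

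**The case against.** The strongest reply is that baseline is the last value before the first infusion, and that a V2 trough is scheduled for every subject. V2 therefore supersedes V1, and the fallback operates only when V2 is missing or, under the protocol's definition in 10.3, not valid. That stands. A reader might infer that the comparison with the previous product is generally biased against BT595. The documents do not support this, because V1 enters only for subjects without a usable V2 value.

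A second reply is that the protocol calls the screening sample a trough, and a sample on Day 0 or just before a prior infusion would be close to one. This also stands in part. A reader might infer that V1 necessarily overstates the trough, but the documents show only that it may. The label expresses an intention that no timing rule enforces.

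Third, other outputs are less exposed than they look. The mean trough figures in SAP 9.6.2 start at the first BT595 dose, 7.2 keeps screening and baseline apart, Table 1 omits screening, and no V1-to-V2 change is planned. All of this is correct. It narrows the problem to the 9.4.1 tables, the 7.2 label and the fallback.

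Fourth, SAP 5.5 and 9.2 allow out-of-window samples to be excluded. That does not resolve the point: the exclusion is discretionary, and a screening sample between Day -28 and Day 0 is inside its own window.

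Early leavers raise a related question. Protocol 4.4 asks for the closing-visit examinations at withdrawal, and SAP 6.4 summarises by nominal visit, so a closing sample may be off-interval. A reader might infer that such values run high. The direction is not fixed: a subject who leaves after a missed infusion could be sampled late and fall below trough.

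**Conclusion.** The point holds as a minor one. The stated rules would summarise screening concentrations of unspecified timing as prior-product troughs, and would allow them into change from baseline and the exploratory 9.7 comparison when V2 is missing. SAP 9.4.1 also disagrees with Table 1 on whether screening belongs in the trough data, and mixes two visit numberings.

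For a random-time draw the average inflation is about 1.2 to 1.6 times trough. This rests on the assumed half-life of 21 to 42 days, mono-exponential decline, no endogenous IgG, and uniform timing. Eligibility requires impaired, not absent, antibody production, and any endogenous IgG would lower these factors. The overall shift in the 9.7 ratio is about 1% to 4% if 5% to 10% of subjects fall back, and larger only in small age-by-schedule cells. The primary endpoint is not touched.

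**What to change.** - In SAP 6.2, 8.2.1, 9.4.1 and 9.7, define the IgG trough baseline as the V2 pre-infusion sample. Allow a V1 or unscheduled value only if it is documented as drawn at the end of the prior dosing interval.
- In SAP 7.2 and 9.4.1, report V1 as a screening concentration, outside the trough tables, in line with Table 1.
- Reconcile the visit numbering in the 9.4.1 tables, so that total IgG and subclass rows follow one system.
- Flag closing samples from early leavers that were not drawn 3 or 4 weeks after the last infusion, and leave them out of the trough summaries. State no direction of bias.

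The cost is SAP wording and a date check. No new samples or visits are needed. Accepting a V1 value does require the date of the relevant prior infusion, or its reconstruction from the V2 scheduling rule. The downside is that a subject with neither a V2 sample nor a documented end-of-interval sample has no IgG baseline and drops out of 8.2.1 change from baseline and 9.7.

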#### 9.4.2. Antigen Specific IgG Trough Concentrations (Specific IgG Trough PK Set)

Trough concentrations for antigen-specific IgG measured only at the central laboratory will be summarized in the same manner as described for the PK Trough Set in Section 9.4.1. Separate listings and summary tables will be provided for this data set.

Summary statistics will not be presented if 50% or more of the actual values for the PK sets at any 1 time point or bin are BLQ or missing or less than 3 values are available. The reporting will be limited to median value for n=1 and to median, min and max values for 1<n≤2.

Additionally, trough concentrations for antigen-specific IgG measured only at the central laboratory will be summarized by dose level and antigen-specificity:

Analyte	Schedule	Age category (years)	Visit	Dose levels	S
Specific	Q3W	12 to <17 (FDA)	V1 (baseline) and	All	dose
	Q4W	12 to <18 (EMA)	V7/V5 (before the	combined	
		17 to <76 (FDA)	7 th /5 th infusion)	Bins:	
		18 to <76 (EMA)		0.2-<0.4	
		17 to <65 (FDA)		0.4-<0.6	
		18 to <65 (EMA)		0.6-0.8	
		>=65 (EMA, FDA)			
		Overall: 12 to <76			

#### 9.4.3. Steady State Trough Concentrations (Multiple PK Sets)

For comparison purpose, steady state trough concentrations ( $C_{ss}$ ), defined as the trough concentration prior to infusion 7 for Q3W schedule and infusion 5 for Q4W, and measured both at local lab and at central lab (Biotest), will be listed for each subject. The steady state trough concentrations will be summarized separately for PK Trough set (local lab) for all subjects and for the Dense PK Subset (central lab) only for subjects participating to steady state PK study combined by age and dosing regimen (Q3W or Q4W). The comparison between local lab and central lab measurements will be done graphically for the subjects in Dense PK Subset as described in Section 9.6.3.

Antigen-specific IgGs will be summarized in a separate table for Specific IgG Trough PK Set.

In addition, steady-state trough concentrations Css of total IgG normalized by dose level i.e. divided by actual administered dose will also be calculated. Latest dose level before measurement will be used for dose normalization.

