4.2 Inclusion Criteria

Only subjects meeting all of the following inclusion criteria will be considered for study inclusion:

Inclusion Criteria	Rationale	Screening	Baseline
 a) Written informed consent/assent obtained from subjects/subjects' parent(s) or legally acceptable representative indicating that they understand the purpose of and procedures required for the study and are willing to participate in it 	Administrative	х	
b) Male or female, aged 2 through 75 years	Administrative	Х	
 c) Diagnosis of PID with impaired antibody production, i.e.: Diagnosis of common variable immunodeficiency (CVID) as defined by the European Society for Immunodeficiencies (ESID)^a/Pan American Group for Immunodeficiency (PAGID)^b diagnostic criteria Or X-linked agammaglobulinemia (XLA) as defined by ESID/PAGID diagnostic criteria 	Disease requirement	х	
 d) Established replacement therapy with any IVIg reference preparation during the previous 6 months, including documentation of IgG trough levels 	Pretreatment requirement	х	
e) Established replacement therapy with a single IVIg reference preparation for at least 3 months prior to treatment start with BT595 at a 3- or 4-week schedule with a constant IVIg dose that did not change by ±20% of the mean dose, regular dosage intervals, and at least 1 IgG trough level of ≥5 g/L during the previous 3 months	Pretreatment requirement	х	Х

^a ESID diagnostic criteria (European Society for Immunodeficiencies, 2006). ^b PAGID diagnostic criteria (Conley et al, 1999).

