#### 9.4.4. Summary of all Dense PK Serum Concentrations (Dense PK Subset)

Similar to the trough concentrations, summary of all serum concentrations of the Dense PK Subset measured in central lab (including the trough concentrations for the dense PK sampling period measured at central lab) will be done by analyte, whole population, age

category, treatment schedule (Q3W/Q4W) and by dosing regimen combining all dose levels. An additional summary will include the split by dose level for the last dose before sampling for dense PK, as presented above with 3 dose ranges (0.2-<0.4, 0.4-<0.6, 0.6-0.8 g/kg). For the summaries based on dosing bins, results for subjects with changes to dose level will be combined after dose adjustment based on dose history. Dose history will include the starting dose level and the adjusted dose level as well as the time of adjustment. If the dose adjustment was done close to the measurement of  $C_{ss}$  the resulting concentration may be excluded from the summary due to insufficient time to reach steady state at the adjusted dose level.

Nominal time points will be used for all summary statistics of PK concentrations. Summaries by age categories (based on the availability of pediatric subjects) will include the Dense PK Subset data for total IgG, IgG subclasses, and antigen-specific IgG. Data will be presented in separate table for each analyte.

Summary statistics will not be presented if 50% or more of the actual values for the Dense PK Subset at any time point are BLQ or missing or if less than 3 values are available. The reporting will be limited to median value for n=1 and to median, min and max values for  $1 < n \le 2$ .

All total IgG concentrations measured in the Dense PK Subset will also be presented as change from "baseline" concentrations with "baseline" defined in this case as a predose concentration before the start of dense PK sampling period. Change from baseline total IgG concentrations will be used in an additional PK analysis. (This definition of this "baseline" concentration will be indicated in appropriate tables, listings, and figures when relevant).

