#### 9.7. EXPLORATORY COMPARISON OF STEADY-STATE TROUGH CONCENTRATIONS FOR TOTAL IGG, IGG SUBCLASSES, AND SPECIFIC IGGS WITH PREVIOUS IGG FORMULATION

Exploratory comparison of  $C_{ss}$  and dose-normalized  $C_{ss}/D$  between BT595 and similar products (IVIG products) will be performed for age categories and overall by ANOVA. The data for PK Trough Set and Specific IgG Trough PK Set will be used.

Log-transformed parameters Css/D for total IgG, IgG subclasses and specific IgGswill be compared separately by dosing interval and by age category where possible with treatment as fixed effect and subject as random effect based on existing guidance on bioequivalence from EMA (European Medicines Agency Questions and Answers: positions on specific questions addressed to Pharmacokinetics and FDA (Food and Drug Administration (FDA) Guidance for Industry). The following hypotheses will be tested for Css values:

Ho1:  $\mu_T/\mu_R \le 80\%$  vs. Ha1:  $\mu_T/\mu_R > 80\%$  and Ho2:  $\mu_T/\mu_R \ge 125\%$  vs. Ha2:  $\mu_T/\mu_R < 125\%$ 

The same model will also be repeated for dose normalized trough concentration.

If the 90% CI for the geometric mean ratio (GMR) is within (80% - 125%) for any of the contrasts for the parameters Css/D, the null hypotheses, that is H01 and H02, will be rejected with conclusion that the administration with BT595 (T=Test) is equivalent to administration of the previous IgG formulation (R=Reference).

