#### The following contrasts will be explored (total IgG and IgG subclasses 1-4):

Q3W schedule - Css/D for 7th infusion vs baseline

Q4W schedule - Css/D for 5th infusion vs baseline

The formula for calculation of the estimated ratio between the test and reference and the  $(1-2^{*}\alpha)^{*}100$  % CI of the ratio is given below.

Difference = Estimate of difference between test and reference least square means  $Ratio = 100 \times e^{Difference}$   $(1-2^{*}\alpha)^{*}100\%$  Cls for the Ratio:  $Lower = 100 \times e^{(LowerBound (1-2^{*}\alpha)\%Cls for the Difference)}$  $Upper = 100 \times e^{(UpperBound (1-2^{*}\alpha)\%Cls for the Difference)}$ 

Comparison between BT595 and previous IVIG products will also be explored graphically with box plots of  $C_{ss}/D$  as described in Section 9.6.5Fehler! Verweisquelle konnte nicht gefunden werden. of the SAP.

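### SAP 9.7 and 9.8 use a dose-normalised trough (Css/D) that divides by the latest dose even when it changed too recently for steady state, and the SAP's own exclusion for this case is not carried into those models.

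*SAP*

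**What the plan says.** - **The quantity.** SAP 9.4.3 takes Css, "defined as the trough concentration prior to infusion 7 for Q3W schedule and infusion 5 for Q4W". The total IgG value "divided by actual administered dose will also be calculated", and the dose to be used is the last one: "Latest dose level before measurement will be used for dose normalization". Whether D is in g or g/kg is not stated.
- **Where it is used.** SAP 9.7 compares Css and Css/D on BT595 with the baseline trough on the previous IVIg (for example, "Q3W schedule - Css/D for 7th infusion vs baseline"), with an 80–125% margin and a 90% confidence interval. A pass is read as equivalence. The analysis sets are named: "The data for PK Trough Set and Specific IgG Trough PK Set will be used". SAP 9.8 compares the same quantities between age groups, with as few as 3 subjects per group.
- **Dose changes on BT595.** Protocol 6.2.1 requires an adjustment if the trough falls below 5 g/L. Protocol 6.1 also allows any medically indicated change, with no direction stated.
- **The reference side.** Inclusion criterion (e) in Protocol 4.2 requires at least 3 months on one product at "a constant IVIg dose that did not change by ±20% of the mean dose".
- **Existing handling.** For the Dense PK Subset, SAP 9.4.4 says that after an adjustment close to the Css measurement "the resulting concentration may be excluded from the summary due to insufficient time to reach steady state". SAP 9.6.1 refers back to 9.4 for dose adjustment in summaries. For the trough sets, SAP 5.5 and 5.6 allow exclusion only for improper dosing or out-of-window sampling.

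**The concern.** A trough taken one interval after a dose change still consists largely of IgG from the earlier doses. Dividing it by the new dose attributes to the product a difference that comes from timing. A protocol-mandated raise is neither improper dosing nor an out-of-window sample, so nothing written for the trough sets removes such a value from the 9.7 and 9.8 models.

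The reference trough is better protected, because it follows at least 3 months on a broadly constant dose. The mandatory trigger on BT595 is a low trough, so raises are the foreseeable direction. Un-normalised Css is not a clean fallback: after a raise it moves up because more drug was given, which is the opposite direction.

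At stake are an exploratory equivalence statement and exploratory age contrasts. The SAP accepts that such values may not be at steady state, but leaves their removal to discretion after the data are seen.

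**Working it through.** The documents give no half-life, dose-change rate or power for this comparison, so there is no plan figure to reproduce.

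**Inputs from the documents**
- Interval τ = 21 or 28 days.
- Css before infusion 7 (21-day) or infusion 5 (28-day).
- D = latest dose.
- Margin 80–125%.

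**Assumptions (not in the documents)**
- Half-life 21–40 days.
- Linear one-compartment build-up, trough proportional to dose at steady state.
- Changes of +25%, +50% or −25%.
- 5–30% of subjects affected.

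**Step 1: one subject.** After a dose change by fraction r, held for k intervals, the trough has moved a fraction f = 1 − 2^(−kτ/t½) towards its new steady state. Observed over true steady-state Css/D is (1 + r·f)/(1 + r).

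Example: τ = 21, t½ = 28, k = 1, so f = 1 − 2^(−0.75) = 0.405. With r = 0.25 the factor is (1 + 0.101)/1.25 = 0.881, or 12% too low.

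Ranges over half-lives of 21–40 days:

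| Change | k | 3-week | 4-week |
|---|---|---|---|
| +25% | 1 | 0.86–0.90 | 0.88–0.92 |
| +50% | 1 | 0.77–0.83 | 0.80–0.87 |
| +25% | 2 | 0.90–0.95 | 0.92–0.97 |
| +50% | 2 | 0.84–0.92 | 0.87–0.95 |
| +25% | 4 | 0.95–0.99 | n/a |
| +50% | 4 | 0.92–0.98 | n/a |
| −25% | 1 | 1.17–1.23 | 1.13–1.20 |

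One interval after a raise of 25–50%, Css/D is therefore 8–23% too low (22% at most if the half-life does not exceed 35 days).

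**Step 2: how many intervals are available.** Protocol 6.2.1 lets a trough change the dose at the following infusion. The first trough on BT595 is taken before infusion 2, so it can act from infusion 3. Before Css, a 4-week subject then receives only infusions 3 and 4 at the new dose (k ≤ 2), and a 3-week subject infusions 3 to 6 (k ≤ 4). SAP 3.7.1 instead describes adjustment at the same infusion, which gives k ≤ 3 and k ≤ 5. A change prompted by a pre-BT595 trough could come earlier still.

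**Step 3: the group ratio.** The 9.7 model works on the log scale within subjects, so if a share p of subjects carries factor b, the ratio is multiplied by b^p.

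- p = 5%, b = 0.95: 0.997, a shift of 0.3%.
- p = 10%, b = 0.80–0.95: 0.978–0.995, a shift of 0.5–2.2%.
- p = 20%, b = 0.861 (25% raise, 3-week, t½ = 40, k = 1): 0.970, a shift of 3.0%.
- Extreme case, p = 30%, b = 0.80: 0.935, a shift of 6.5%.

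With b = 0.80, all subjects (p = 1) would have to be affected before a true ratio of 1.00 reached the 0.80 limit.

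**Step 4: small age cells in 9.8.** With n = 3 and one affected subject, p = 1/3. Then b = 0.861 gives 0.951 and b = 0.80 gives 0.928, a shift of 5–7% in that cell.

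**The case against.** **The SAP already handles this.** In part. SAP 9.4.4 names the problem, 9.6.1 refers summaries back to 9.4, individual trough plots identify subjects with dose changes (9.6.2), and adjustments are tabulated by infusion number (section 10). What remains open is whether the 9.7 and 9.8 models inherit the exclusion, and with what limit.

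**Css/D is not biased in one direction or on one side only.** This stands. A reader might infer that BT595 is systematically disadvantaged. The documents do not support that: dose may change for any medical indication, reductions push Css/D up, and a low trough on the previous IVIg can also prompt a raise, since criterion (e) needs only one trough of at least 5 g/L. The reference dose may vary by up to 20% around its mean, and the SAP does not say which prestudy dose is D at baseline. SAP 9.8 has no reference product; there the error matters only if changes differ in share or timing between age groups.

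**Dropping changed subjects creates its own bias.** This also stands. Mandatory raises follow low BT595 troughs, so removing those subjects can favour BT595. A restricted analysis should not replace the all-subjects one.

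**The one-interval case is the worst case, and the analysis is exploratory.** Both are true. SAP 9.7 is headed exploratory, and Protocol 10.10 plans the intra-individual comparison without a formal test.

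**Conclusion.** The concern holds as a limited gap in an exploratory analysis. The latest-dose rule misstates Css/D for subjects with a recent change: about 8–23% too low one interval after a 25–50% raise, and about 13–23% too high one interval after a 25% cut. With two intervals on the new dose, the longest a 4-week subject can have under the Protocol 6.2.1 timing after a BT595 trough, raises of this size still leave Css/D 3–13% low.

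A group shift of about 0.3–3% rests on 5–20% of subjects being affected, mainly by moderate raises. Larger or more frequent recent raises would exceed it; small age cells are more sensitive. All figures assume proportional one-compartment kinetics and a half-life of 21–40 days.

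A reader might infer that the equivalence conclusion is unsafe. The documents do not support that: the shift is small against an 80–125% margin, and the number of dose changes is unknown. The primary endpoint is untouched.

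**What to change.** 1. In SAP 9.7 and 9.8, pre-specify an analysis that excludes subjects whose g/kg dose or dosing interval changed within a fixed number of intervals before the infusion 7/5 predose sample. Fix the number for each schedule before the data are reviewed.
2. Report it side by side with the all-subjects result, with the number excluded per cell. Base any equivalence statement on agreement of the two, because exclusion alone can favour BT595.
3. In SAP 9.4.3, give the unit of D and state which prestudy dose is D for the baseline trough.
4. Reconcile the timing of dose adjustment: Protocol 6.2.1 and the introduction to SAP section 8 place it at the following infusion, while SAP 3.7.1 describes it as immediate. The timing determines how many intervals precede Css.

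Cost: SAP wording and one filter on dose-change data that Protocol 6.2.1 already requires in the eCRF. A few subjects leave one of two exploratory analyses, and some age cells may fall below the minimum of 3. No dosing rule changes.
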